8.4.2 Analysis of Rescue Medication and Concomitant Medication

Rescue and concomitant medications will be classified by the World Health Organization (WHO) Drug dictionary, and numbers and percentages of subjects receiving each classified medication will be calculated for all medications.

8.5 Analysis of Efficacy

8.5.1 General Inferential Principles

All efficacy analyses will be conducted using the mITT and PP populations by randomized treatment group and, unless stated otherwise for equivalence analysis, all tests are two-tailed at a significance level of $\alpha = 0.10$ with 90% confidence intervals (CIs). For the superiority analysis compared Lubiprostone sprinkle and capsule formulations to the matching Placebo, all tests are two-tailed at a significance level of $\alpha = 0.05$. Analysis of covariance (ANCOVA) and the van Elteren test will be performed to compare the sprinkle and capsule formulations of lubiprostone with matching placebo.

8.5.1.1 Missing Data

Only observed SBM count will be adjusted for missing data, and the missing data imputation will be performed using the following four methods:

Last Daily Observation Carried Forward (LDOCF): Subjects with any missing daily observed SBM count during the treatment week will have their daily value(s) imputed by carrying over the previous non-missing post-baseline SBM observed count, and the LDOCF method will be used for the primary efficacy analysis.

Average Daily Baseline Observation Carried Forward (BOCF): Subjects with any missing daily observed SBM count during the treatment week will have their daily value(s) imputed by the Baseline SBM observed count divided by 7.

Observed Case (OC) Analysis: All observed SBMs that occurred during Week 1 for each subject will be counted, without any missing data imputation being performed.

Regression Imputation: Subjects with missing Week 1 observed SBM count will have their value imputed using the regression equation found from regressing the Week 1 observed SBM count as the dependent variable for all subjects in the same treatment group on their baseline observed SBM count as the independent variable.

Median Imputation: The median observed SBM count for all subjects in the same treatment group will replace missing observed SBM count at Week 1.

BOCF, OC Analysis, Regression Imputation, and Median Imputation will be used as sensitivity assessments of the primary efficacy endpoint.

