8.1 Determination of Sample Size

This is a phase 3, multicentre, double-blinded, randomized, placebo-controlled study evaluating the bioequivalence of Sprinkle and Capsule formulations of lubiprostone when administered orally in subjects with chronic idiopathic constipation. Subjects will be randomized (1:1:1 ratio) to receive either lubiprostone sprinkle, lubiprostone capsule or matching placebo BID in a blinded, double-dummy fashion.

In clinical studies of the lubiprostone capsule formulation during the CIC development program, the average observed SBM count at Week 1 for lubiprostone 24 mcg BID was 5.62 with a standard deviation of 4.24. In order to achieve the conclusion of equivalence between the sprinkle and capsule formulations of lubiprostone, the 90% confidence interval for the ratio of means has to be contained within the interval of [0.8, 1.25]. Thus, a sample size of 156 per group is required to achieve 90% power at a 10% significance level.

Assuming 10% of subjects do not meet criteria for inclusion in the Per Protocol population and/or do not have observed week 1 SBM count due to early withdrawal or other reasons, 174 subjects per treatment group (a total of 522 subjects) will be required for this study.

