8.2 Datasets Analysed

Four analysis populations, the modified Intent-to-Treat (mITT) population, the Per Protocol (PP) population, the Completers population, and the Safety population, will be defined as follows:

- **The mITT population** will include all randomized subjects who take at least one dose of study medication and have at least one diary entry. This dataset will be used for summarization of demographic and baseline characteristic data, and for all efficacy analyses.
- **The PP population** will consist of all mITT subjects who met all eligibility (i.e., inclusion/exclusion) criteria at study entry, did not have any major protocol violations, had an overall diary compliance of at least 70%, and had a dosing compliance within 75% to 125%. Dosing compliance will be verified by the use of diary data. Supportive efficacy analyses will be performed on this population to evaluate the impact of major protocol violations.
- **The Completers population** will consist of only those subjects who complete the entire treatment period of the study with a recorded primary endpoint and will be used for supportive efficacy analyses.

- **The Safety population** will consist of all randomized subjects who take at least one dose of double-blinded study medication. Analyses on the Safety population will be based on the actual treatment received.

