SBM frequency rate at week 1 will be summarized by treatment group. The 90% CIs of the treatment ratio between the sprinkle and capsule formulations will be calculated. ANCOVA, using Week 1 SBM frequency rate as the dependent variable will be used to compare treatment groups with baseline SBM frequency rate as a covariate. The van Elteren test stratified baseline SBM frequency rate (< 1.5 or ≥ 1.5) and pooled sites will be performed to detect differences from baseline for lubiprostone sprinkle and lubiprostone capsule vs. matching placebo.

In order to adjust for early withdrawals or missing days, subjects with less than 7 days of treatment will have the Week 1 SBM frequency rates adjusted as follows:

$$7 \times \text{Number of SBMs} / (\text{Number of days treated}).$$

If the number of observed days is less than 4 days, then the data will be considered insufficient and the rate will be missing for that subject. No imputation will be performed for missing data.

8.5.3.5 Mean Change from Baseline in SBM Frequency Rate at Week 1

Changes from baseline in SBM frequency rate at week 1 will be summarized by treatment group. The 90% CIs of the treatment ratio between the sprinkle and capsule formulations will be calculated. ANCOVA for the change from baseline in observed SBM count and the van Elteren test stratified by baseline SBM frequency rate (< 1.5 or ≥ 1.5) and pooled sites will be performed for the following comparisons:

- The sprinkle formulation of lubiprostone vs. the placebo group
- The capsule formulation of lubiprostone vs. the placebo group

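### The Observed Case sensitivity analysis sums whatever days were recorded, which is the same as scoring every missing day as zero

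*Combined protocol and SAP*

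**What the plan says.** Section 8.5.1.1 gives LDOCF the deciding role: "the LDOCF method will be used for the primary efficacy analysis". Section 8.5.2 places that analysis in the per-protocol (PP) population. The other methods are checks on it: "BOCF, OC Analysis, Regression Imputation, and Median Imputation will be used as sensitivity assessments of the primary efficacy endpoint". The OC rule reads: "All observed SBMs that occurred during Week 1 for each subject will be counted, without any missing data imputation being performed". No divisor, minimum or exclusion is attached to it.

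Short weeks are handled only for a different endpoint, the SBM frequency rate in Section 8.5.3.4: "subjects with less than 7 days of treatment will have the Week 1 SBM frequency rates adjusted as follows". The formula there is 7 × SBMs / days treated, and the rate is missing when fewer than 4 days were observed.

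Section 8.5.1 runs all efficacy analyses in both mITT and PP. Section 8.2 admits to mITT randomized subjects who "take at least one dose of study medication and have at least one diary entry", without saying whether that entry must follow the first dose. PP requires at least 70% overall diary compliance.

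**The concern.** A subject with three recorded days contributes a three-day total to a mean made up mostly of seven-day totals. The method is labelled as free of imputation, yet it gives the same number as filling each missing day with zero, the lowest value a count can take.

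This matters because OC is meant to show whether the equivalence conclusion depends on how missing days are handled. If one formulation loses more days, that loss appears as a lower SBM count for that formulation. With truly equal formulations, this pushes the ratio away from 1. If the formulation with the higher true count also loses more days, it pulls the ratio back toward 1 and can make non-equivalent products look equivalent.

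**Working it through.** **Inputs from the documents.** Section 8.1 states that "the average observed SBM count at Week 1 for lubiprostone 24 mcg BID was 5.62 with a standard deviation of 4.24". The 90% CI for the ratio of means must lie within 0.8 to 1.25. The stated size is 156 per group, or 174 after a 10% allowance.

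**The plan's own figure.** The plan gives no figure for the OC analysis, so the nearest check is the sample size. CV = 4.24/5.62 = 0.754, and log-scale SD = √ln(1 + 0.754²) = 0.671. Exact two one-sided t-tests with margin ln 1.25, true ratio 1 and 90% power give n = 156 at 0.10 per side. Then 156/0.90 = 173.3, rounded up to 174. (At 0.05 per side, which a 90% CI implies, 156 gives about 80% power. That is a separate matter and plays no part below.)

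**Step 1: the identity.** The sum over recorded days equals the seven-day sum with 0 on each unrecorded day. In eight simulated scenarios the OC count and an explicit zero-fill gave identical results.

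**Step 2: loss per subject.** With k missing days and a constant daily rate, the expected OC count is 5.62 × (7 − k)/7. For k = 1 to 6 this is 4.82, 4.01, 3.21, 2.41, 1.61 and 0.80.

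**Step 3: how large k can be.** If the 70% PP rule applies to the treatment week, at least 5 of 7 days are needed (5/7 = 71%, 4/7 = 57%), so k ≤ 2. If overall compliance also covers 14 screening days, 0.70 × 21 = 14.7, so 15 of 21 entries suffice and k can reach 6. Dosing compliance does not remove early stoppers either: Section 8.4.1 takes expected doses as exposure days × 2, and Section 8.5.4 speaks of PP subjects who discontinued early. In mITT, k can also reach 6.

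**Step 4: shift in the ratio.** If fractions f_S and f_C of the sprinkle and capsule arms lose k days, unrelated to their SBM rate, the ratio is multiplied by (1 − f_S·k/7)/(1 − f_C·k/7). The rates are assumptions:

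- Extra 10% of one arm, k = 2: 1 − 0.10 × 2/7 = 0.971. Extra 20%: 0.943.
- Extra 10%, k = 6: 0.914. Extra 20%: 0.829.
- 15% vs 5% stopping after Day 3 (k = 4): (1 − 0.15 × 4/7)/(1 − 0.05 × 4/7) = 0.941. For 10% vs 2%: 0.954.
- Share of the log margin used at 0.941: ln 0.941/ln 0.80 = 0.27.
- Extra fraction needed to move a true ratio of 1 to 0.8: 0.2/(k/7), which is 70% at k = 2 and 23% at k = 6.

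**Step 5: simulation.** Gamma-Poisson counts (mean 5.62, SD 4.24), 174 per arm, 3,000 runs, with affected subjects losing the last 2 to 6 days. Scaled means 7 × SBMs / observed days, missing below 4 days.

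| True ratio | Incomplete, sprinkle vs capsule | OC ratio | Scaled ratio | Equivalence declared: OC | Scaled |
|---|---|---|---|---|---|
| 1.00 | 10% vs 10% | 1.00 | 1.00 | 67% | 70% |
| 1.00 | 20% vs 10% | 0.94 | 1.00 | 52% | 68% |
| 1.00 | 20% vs 0% | 0.89 | 1.00 | 33% | 68% |
| 1.25 | 10% vs 0% | 1.18 | 1.25 | 18% | 5% |
| 1.25 | 20% vs 0% | 1.11 | 1.25 | 41% | 5% |

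Complete data gave 72% to 74% at a true ratio of 1 and 5% at 1.25. LDOCF showed no comparable shift: its mean ratios stayed within 0.005 of the true value. Only the contrasts between columns matter here.

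**Step 6: equal missingness.** In the same model, 15% stopping after Day 3 lowers the variance from 17.98 to 17.30 and the mean from 5.62 to 5.62 × (1 − 0.15 × 4/7) = 5.14. The CV rises from 0.754 to 0.809, so precision of the ratio falls although the variance does not rise.

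**The case against.** OC decides nothing: LDOCF in PP does. Section 8.5.1.1 says openly that nothing is imputed. Section 8.5.3.4 already provides a rate adjusted for short weeks with a 90% CI for the sprinkle-to-capsule ratio, and Section 8.2 adds a Completers population. Detail may still come in the SAP, which Section 8 says will be finalised before unblinding. All of this limits the weight of the point. It does not repair the OC rule: the frequency rate is a separate endpoint, and because it divides by days treated, diary days skipped while on treatment stay uncorrected there too.

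The size depends on assumed missingness, and the only planning figure is a combined 10% for PP exclusions and missing counts. That stands. So does the fact that the diary (Appendix 3) lets a subject enter a bowel movement from the day before, so one skipped evening need not be a lost day.

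Two stronger readings are not supported:

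- A reader might infer that a dosed subject with no post-dose diary stays in mITT and scores 0 SBMs. The mITT wording permits this, but the regression and median methods in Section 8.5.1.1 recognise a missing Week 1 count, and such a subject fits that class at least as well. Section 6.1.2.2 also has the first dose time entered in the diary at the clinic.
- A reader might infer that equal missingness inflates the variance. Step 6 shows that under a plausible count model only the CV rises.

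**Conclusion.** The concern holds for the OC sensitivity analysis as written. It is a zero-fill analysis under another name, and its ratio is biased when missing days differ between sprinkle and capsule. Modest imbalances (an extra 10% to 20% of one arm missing two days, or 15% versus 5% stopping after Day 3) multiply the ratio by 0.97 to 0.94. Larger imbalances in mITT could do more. The bias can hide a difference as well as create one. These sizes rest on assumed missingness, a constant daily rate, and missingness unrelated to SBM rate. With equal missingness the ratio stays at 1.00.

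A reader might go further and conclude that the primary equivalence result is compromised. The documents do not support that, because the primary analysis uses LDOCF and not this count. The point should be corrected in the SAP, but it does not threaten the trial's main conclusion.

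**What to change.** In the SAP, before unblinding:

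1. Define the OC value as 7 × SBMs / number of treatment days covered by diary reports. A day is covered by its own evening report or by the look-back in the next day's report. This should not depend on whether a bowel movement was entered. Dividing by days with an entry alone would bias the value upward: one skipped evening whose SBMs were all entered the next day would inflate the value by 7/6 = 1.17.
2. Set the value to missing when fewer than 4 days are covered, matching Section 8.5.3.4, and report the number set to missing by arm.
3. Keep the raw sum only if it is relabelled as a zero-fill analysis.
4. Use the same definition of a missing Week 1 count for the regression and median methods, which at present do not say when a partial week counts as missing.
5. Separately, state that the mITT diary condition in Section 8.2 means at least one post-dose bowel-habit report. A dosing-time entry alone should not satisfy it.

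The cost is wording, but it has consequences. Subjects with fewer than 4 covered days leave this analysis, possibly unequally by arm. In the Day 3 scenario all affected subjects would go, about 0.15 × 174 = 26 sprinkle against 0.05 × 174 = 9 capsule, so the counts by arm are needed to read the result. The mITT clarification reaches every mITT analysis, including the baseline summaries, though probably for few subjects.

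### Regression and median imputation give each missing Week 1 count one fixed value with no variance correction specified, so two supporting 90% intervals would be somewhat too narrow, in the direction of equivalence

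*Combined protocol and SAP*

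**What the plan says.** Section 8.5.1.1 assigns LDOCF to the primary analysis and then states: "BOCF, OC Analysis, Regression Imputation, and Median Imputation will be used as sensitivity assessments of the primary efficacy endpoint".

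Two of these four fill in a whole-week count. Under regression imputation the missing value is "imputed using the regression equation found from regressing the Week 1 observed SBM count as the dependent variable", with baseline count as the predictor, within the same arm. Under median imputation, "The median observed SBM count for all subjects in the same treatment group will replace missing observed SBM count at Week 1". Each missing subject therefore receives one deterministic value. Sections 8.5.1.1, 8.5.2 and 8.5.4 mention no residual draw, multiple imputation, bootstrap or variance adjustment. Section 8 leaves further detail to a SAP to be finalised before unblinding, and the text available contains no variance rule.

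Under Section 8.5.2, equivalence is claimed if the 90% interval for the sprinkle/capsule ratio lies within [0.8, 1.25], in the PP population. Section 8.5.1 also calls for efficacy analyses in mITT.

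The documents give no expected share of missing Week 1 counts. The 10% allowance in Section 8.1 covers PP exclusions and missing counts together. Nor do they say when a Week 1 count is missing. The only threshold, fewer than four observed days, is in Section 8.5.3.4 and concerns the SBM frequency rate.

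**The concern.** A value taken from a regression line or an arm median has no scatter of its own, yet it enters the analysis as a full observation. The standard deviation shrinks while the sample size rises to the full count, so the reported standard error falls below the true one.

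In an equivalence trial this error favours the claim: a narrower interval fits more easily between 0.8 and 1.25. Both methods also assume that missing subjects resemble the observed subjects in their own arm, so the regression version stays close to the observed-case estimate with a tighter interval around it. Agreement with the primary result could then be reported as robustness that the data do not support.

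**Working it through.** **Inputs.** From Section 8.1: "the average observed SBM count at Week 1 for lubiprostone 24 mcg BID was 5.62 with a standard deviation of 4.24"; 174 randomized per arm; limits 0.8 and 1.25. From Sections 8.1 and 8.5.2: a 90% interval, which is two one-sided tests at 5% each, so 5% is the benchmark at each limit. Assumed, because the documents are silent: the missing share *f*, data missing completely at random, and the shape of the count distribution.

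**The plan's own figure.** Section 8.1 says that "a sample size of 156 per group is required to achieve 90% power at a 10% significance level". CV = 4.24/5.62 = 0.754, and log-scale SD = √ln(1 + 0.754²) = 0.671. With a true ratio of 1 and one-sided 10% per test, n = 2 × 0.671² × (1.2816 + 1.6449)² / (ln 1.25)² ≈ 155, or 156 with the t distribution. Then 156/0.9 rounds up to 174, and 3 × 174 = 522. So the inputs are read correctly. The 156 depends on 10% per one-sided test, whereas a 90% interval means 5% per test; that is a separate matter and does not alter the 5% benchmark used here.

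**Closed form for filling in an arm mean.** The completed data have variance about (1 − f)s² and size n, so the reported SE² is (1 − f)s²/n. The true SE² is s²/[n(1 − f)]. Their ratio is (1 − f)², so reported SE / true SE ≈ 1 − f, and

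false-pass rate at a limit ≈ 1 − Φ(1.645 × (1 − f)).

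At f = 0.10: 1.645 × 0.90 = 1.48, which gives 6.9% and interval coverage of 86.1% instead of 90%.

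**Simulation.** 174 per arm; gamma, lognormal or negative-binomial counts; latent correlation with baseline 0 or 0.4; Fieller-type pair of one-sided tests; 6,000 to 20,000 runs per cell. Monte Carlo standard error near 5% is √(0.05 × 0.95/6,000) = 0.28 percentage points at most. False-pass rate at a true ratio of 0.80 or 1.25:

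| Missing share (assumed) | Closed form | Regression | Median |
|---|---|---|---|
| 2% | 5.35% | 5.1–5.4% | 5.0–5.4% |
| 5% | 5.9% | 5.6–5.9% | 5.3–5.9% |
| 10% | 6.9% | 6.4–6.8% | 5.9–6.7% |
| 20% (hypothetical) | 9.4% | 8.7–9.6% | 7.7–9.2% |

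Observed-case analysis stayed at 4.5–5.1%. At 10% missing, with correlation 0.4, the reported SE was about 0.92 of the true SE, and the interval was 9–10% narrower than with observed cases. A separate simulation with a delta-method interval on the log ratio (8,000 trials) gave 6.5% for both methods at 10% missing, with coverage of 86–87%.

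**Truly equivalent products.** At a true ratio of 1 with 10% missing (negative-binomial counts), the pass rate was about 74% with regression and 72–73% with median imputation, against about 67% with proper multiple imputation. The extra 5 to 7 points are false precision.

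**Unequal missingness (5% in one arm, 15% in the other; assumed).** Median imputation passed falsely about 9% of the time at one limit and 4.5–4.7% at the other, because the ratio itself moves. Regression gave 6.2–6.6%.

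**After the fix.** Multiple imputation with parameter and residual draws (20 imputations, Rubin's rules) gave 4.7–4.9%, 4.7–5.1% and 4.5–5.0% at 5%, 10% and 20% missing. The form tested was a linear regression on baseline; a count model using daily counts was not simulated.

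**The case against.** The strongest reply is that nothing decisive rests on these intervals. LDOCF in the PP population carries the claim, and a narrow sensitivity interval cannot rescue a failed primary result. This stands. A reader might infer that the trial's own false-equivalence rate exceeds 5%; the documents do not support that, because the rates above belong to supporting analyses only.

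The second reply is that the effect may be small. The 10% allowance includes PP exclusions, PP requires at least 70% diary compliance (Section 8.2), and under the observed-case rule a subject with a partial diary still has a count. If missing means no Week 1 diary data at all, the PP share should be low and the excess at 2% is negligible. This also stands, and a 20% share has no basis in the documents. The opposite is possible too: if any missing day makes the week missing, the share could be larger. The mITT analyses, which need only one dose and one diary entry, may also have more missing counts.

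Third, the plan never says that an ordinary variance will be used. That is so; it is the natural reading of the text, but the exact statement is that no correction is specified.

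Fourth, the median of a skewed count lies below its mean, and a reader might infer a biased ratio in all cases. With equal missingness the shift largely cancels between arms; it matters only when missingness differs.

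Finally, the observed-case analysis on the same list is near nominal when data are missing completely at random, so a valid comparator exists. That limits the harm but does not make the other two intervals correct.

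**Conclusion.** The point holds for two of the four missing-data sensitivity analyses. As specified, and analysed with an ordinary variance, their 90% intervals are too narrow in the direction that favours equivalence. The size is modest: a false-pass rate of about 5–5.5% at 2% missing, 5.3–6% at 5% and 6–7% at 10%, against a nominal 5%. The 10% case assigns the entire planned loss to missing counts; the 8–9.5% seen at 20% is hypothetical. These figures assume data missing completely at random and 174 per arm. The consequence is an over-reassuring robustness statement, not an invalid primary conclusion. It is worth correcting before the SAP is finalised because the direction is unhelpful and the remedy is cheap.

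**What to change.** Replace regression and median imputation with one proper multiple-imputation analysis: a count model fitted by arm, with baseline SBM count and observed daily counts as predictors, results combined by Rubin's rules, and the 90% interval for the ratio formed from the combined variance. An acceptable alternative is to keep the imputation but take the interval from a bootstrap that repeats the imputation in every resample. In either case, state in Section 8.5.1.1 when a Week 1 count is treated as missing, and how the variance of the ratio is computed.

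The cost is SAP wording, modest programming and slightly wider sensitivity intervals; no new data and no change to the primary analysis are needed. Multiple imputation of this kind still assumes data missing at random, so it corrects the width of the interval without testing departures from that assumption.
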